assessed using a widely employed salivary testing technique. Briefly, we will ask that participants chew a paraffin tablet (Orion Diagnostica) for 5 minutes after which the participant will be asked to spit into a 50mL tube until 5mL of saliva is collected. We have experience with this non-invasive assessment⁶⁹, with the assessment taking no longer than 5-10 minutes overall and presenting no greater than minimal risk. Other secondary outcomes are necessary to measure to ensure we can properly control for confounding. Dietary composition will be assessed via 3 phone-based dietary recalls during the run-in phase, and again during the final two weeks of the study. We will use these dietary recalls collected during the run-in period to develop personalized 3-day meal plan to standardize individual dietary behavior prior to stool sample collection. Employing dietary recalls at these time points will also allow us to adequately statistically control for participants' dietary changes—changes which, if not controlled, might confound study results.^{70,71} Physical activity will be measured for the duration of the study using the Fitbit Inspire 2 smartwatch that uses accelerometry to measure physical activity metrics such intensity, steps, etc. Finally, anthropometric outcomes will include height, weight, and body composition. These measures, along with the other secondary outcomes aside from PA and Dietary composition, will be measured at the end of the 3-week run-in phase, and at the end of the 4th and 8th study weeks.

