5.2 **Study Procedures:** All eligible and consented participants will complete a 3-week run-in phase during which baseline outcome assessments will be performed. During run-in weeks 1 and 2, participants will wear a Fitbit Inspire 2 smartwatch and complete three unannounced dietary recalls. During the run-in week 3 (see table below), participants will consume their 3-day standardized meal plan on days three through five, obtain a fecal sample, and complete a study assessment visit. To quantify compliance with the 3-day meal plan, participants will be provided with a paper checklist of all foods to be consumed, and will be asked to indicate which foods were consumed and to document any deviation. The study assessment visit will include a fasting blood draw, blood pressure in triplicate, weight measure and body fat assessment in duplicate, and a saliva sample. Following successful completion of all measures, participants will then be randomized into one of the two study groups using PROC PLAN (SAS 9.4) and a 1:1 allocation ratio.

Group 1 (Experimental group): Participants will complete 3 treadmill walking sessions/week (24 total sessions) over 8 weeks at or around their home or in-person within the Epidemiology Clinical Research Center. Each walking sessions will be 30 min in duration during intervention weeks 1

MEDICAL PROTOCOL (HRP-590)

PROTOCOL TITLE: Exercise and the Gut Microbiome R21

VERSION DATE: 05/11/2022

through 4 and 45 min during intervention weeks 5 through 8. Notably, this exercise dose (i.e., intensity x session duration x weekly frequency x intervention length) is equivalent to, or greater than, that employed in most existing human studies of exercise and the gut microbiome in addition to the exercise dosage observed necessary to yield meaningful cardiometabolic changes.⁷² Therefore, while the dose is 'modest', it reflects what is relevant in real-world interventions and appropriate for overweight or obese sedentary individuals.

During week 4, participants will again consume their 3-day standardized meal plan, obtain a fecal sample, and complete a study assessment visit (same measures as described above for the 3-week run-in, except no fasting blood draw will be taken).

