During weeks 7 and 8, participants will complete 3 unannounced phone-based dietary recalls. During week 8, participants will again consume their 3-day standardized meal plan, obtain a fecal sample, and complete a study assessment visit (same measures as described above in run-in week 3).

Table 1. Timing of Data Collection events during the 3-Week Run-In and Intervention Weeks 4 & 7/8.

Day 1	Day 2	Day 3	Day 4	Day 5	Day 6	Day 7
				Stool (pm)*	Stool (am)*	Stool
		Standard Diet Day1	Standard Diet Day2	Standard Diet Day3		
						Assess. Visit

**Preferred timing stool collection is the evening of Day 5 or morning of Day 6, though anytime in the Day 5 – 7 window is acceptable.*

Group 2 (Control group): Participants will be asked to maintain their usual PA during the initial 8-week intervention period but will undergo all data collection procedures as outlined above for the experimental group.

Expanded Data Collection Procedures: We have two **Primary Outcomes**.

The first primary outcome is changes to the gut microbiome, assessed via metagenomic sequencing, from pre- to post-intervention (**Specific Aim 1**). The Shannon Index will be our primary indicator for changes in gut microbiota composition. Participants will use the OMNIgene-Gut stool collection kit to obtain their fecal samples collected at baseline, week 4 and

MEDICAL PROTOCOL (HRP-590)

PROTOCOL TITLE: Exercise and the Gut Microbiome R21

VERSION DATE: 05/11/2022

week 8. The home-collected samples will be returned to our lab within 30 days. DNA will be extracted from the stool samples using the 96 well plate Mo Bio Power soil kit on an Epmotion robot and eluted into 50ul aliquots. Each extraction will contain negative and positive controls representing defined bacterial communities (Zymo; Irvine, CA). DNA will be quantified using Quant-it and stored at -80°C. Metagenomic libraries will be prepared at the *UMN Genome Center* (see 'Facilities' document) using the Nextera XT kit (Illumina; San Diego, CA) and barcoded. DNA libraries will be denatured with NaOH and diluted to 8-12 pM in Illumina's HT1 buffer, spiked with 1% PhiX and a HiSeq 1x100 cycle v3 kit Illumina HiSeq, with an expected output of at least 0.5 million total sequences per sample. This approach has been shown to be valid⁵⁴ and represents an approach that can address both gut microbial taxonomy and community functional content at a cost similar to 16S studies.

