collected. The oral microbiome will be assessed using a widely employed salivary testing technique. Participants will be asked to drool into a 50mL tube until 5mL of saliva is collected. For participants that are having difficulty generating saliva, we will ask those participants chew a small piece of orthodontic wax for 5 minutes and then drool into the 50mL tube. We have experience with this non-invasive assessment⁶⁹, with the assessment taking no longer than 5-10 minutes overall and presenting no greater than minimal risk. Other secondary outcomes are necessary to measure to ensure we can properly control for confounding. Dietary composition will be assessed via 3 phone-based dietary recalls. These recalls will be performed on 2 weekdays and 1 weekend day by trained interviewers. Assessment of diet on multiple days allows us to capture the individual variation in participants' diets.⁷¹ We will use these dietary recalls to develop personalized 3-day meal plan to standardize individual dietary behavior prior to stool sample collection. Although randomization should lead to approximately balanced groups with respect to diet, employing dietary recalls at these time points will allow us to adequately statistically control for participants' dietary changes—changes which, if not controlled, might confound study results.^{70,71} Physical activity will be measured during the duration of the study using the Fitbit Inspire 2 smartwatch. Finally, anthropometric outcomes will include height measured using a Seca stadiometer (Seca; Hamburg, Germany), with weight and body composition measured using the Tanita TBF-300a Body Composition Analyzer (Tokyo, Japan).

To collect blood samples and saliva samples as well as body weight, body fat percentage, and blood pressure, we are proposing to employ the following procedures in the designated settings while following all necessary COVID-19 precautions:

Setting: Baseline, week 4, and week 8 visits will occur in the Epidemiology Clinical Research Center (ECRC). We will follow all UMN, OVPR and ECRC approved guidelines for conducting research during the COVID-19 pandemic.

COVID-19 Screening: Participants will complete the OVPR-approved ECRC COVID-19 phone screener the day prior to their visit. Prior to entering the ECRC, participants will call the study coordinator and complete the screening questionnaire again. Upon entry into the building, study staff will assess the participant's temperature.

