15.3 Statistical Analysis: Aim 1 analysis: Gut microbiome data, derived via metagenomic sequencing, will be operationalized as described above. In a primary analysis, generalized linear regression models will regress Shannon Index on intervention assignment. The model is formalized as: $E[Y] = \text{intercept} + \beta_1 * A + \beta_2 * C$. $E[Y]$ =expected Shannon value; β_1 =coefficient for intervention arm; β_2 =coefficient for a vector of confounders should this be necessary in our randomized design. Secondary analyses will consider metagenomic features (genes and functional profiles). Any metagenomic features not present at >0.1% relative abundance in at least 10% of samples will be removed. Zero-inflated log-linear generalized linear models with a Gaussian error term will be fitted, with treatment status as predictor, as implemented by the metagenomeSeq Bioconductor package for shotgun metagenomic data analyses.⁹³ The generalized model, per metagenomic outcome, is formalized as: $\log E[Y] = \text{intercept} + \beta_1 * A + \beta_2 * C$. $E[Y]$ =expected normalized sequence count value; β_1 =coefficient for intervention arm; β_2 =coefficient corresponding to the vector of baseline confounders. Total read count is incorporated as an offset term. This analysis will generate a “top list” of genes, gene families, and pathways with altered abundance by intervention assignment. Separate models will

MEDICAL PROTOCOL (HRP-590)

PROTOCOL TITLE: Exercise and the Gut Microbiome R21

VERSION DATE: 05/11/2022

be developed for intervention status predicting week 4 and week 8 outcomes. We will also consider time*treatment status models to incorporate stool sampling at all three timepoints. P-values will be corrected for multiple hypothesis testing using the false-discovery rate as we have done previously with high dimensional data.^{86-92,94-98}

Aim 2 analysis: As with Aim 1, generalized linear regression models will be used. Each of three SCFAs (acetate, butyrate and propionate) will be regressed on intervention assignment. The model is formalized as: $E[Y] = \text{intercept} + \beta_1 * A + \beta_2 * C$. $E[Y]$ =expected SCFA value; β_1 =coefficient for intervention arm; β_2 =coefficient for a vector of confounders.

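### Sections 3.2 and 5.2 intend to control for dietary change, which is partly post-randomisation, and the primary Aim 1 and Aim 2 models in 15.3 do not exclude it

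*Combined protocol and SAP*

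**What the plan says.** Section 3.2 assesses diet through "3 phone-based dietary recalls during the run-in phase, and again during the final two weeks of the study". It gives the purpose directly: "Employing dietary recalls at these time points will also allow us to adequately statistically control for" participants' dietary changes, described as "changes which, if not controlled, might confound study results". Section 5.2 grants that randomisation should roughly balance the groups on diet, then repeats the purpose: "employing dietary recalls at these time points will allow us to adequately statistically control for" dietary changes.

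Section 5.2 also fixes the timing. Baseline measures are taken in a three-week run-in, and then: "Following successful completion of all measures, participants will then be randomized into one of the two study groups". The second set of recalls falls inside the intervention: "During weeks 7 and 8, participants will complete 3 unannounced phone-based dietary recalls".

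Section 15.1 refers the reader to 15.3 for the analysis plan. No model there names diet. The covariates are:

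- Aim 1 primary model (Shannon Index): "coefficient for a vector of confounders should this be necessary in our randomized design", with no members listed.
- Aim 1 secondary models for metagenomic features: "coefficient corresponding to the vector of baseline confounders", again unlisted but restricted to baseline.
- Aim 2 models (three SCFAs): a vector of confounders with no members, no condition and no restriction to baseline.
- Aim 3 mediation model: age, sex, race/ethnicity and PA duration.

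**The concern.** Aims 1 and 2 ask for the effect of eight weeks of walking against control. Randomisation answers that question without any help from variables that arise later. A variable measured after assignment cannot have caused the assignment, so it cannot confound this contrast, and the reason given in 3.2 and 5.2 does not apply to it.

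Dietary change may, however, be a consequence of exercise. Adjusting for it would then remove whatever part of the effect runs through eating. Where diet and outcome share unmeasured causes, adjustment would also bring back an imbalance that randomisation had removed. Both primary outcomes are exposed: their covariate rule is looser than that of the secondary feature models, and dietary change is the variable the protocol twice says it wants to control. An analyst following the text could reasonably enter it, and could make that choice after seeing the data.

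**Working it through.** The plan offers no figure on this point to reproduce. The check is one of timing, then of which models are open, then of algebra.

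**1. Timing.** Dietary change = (weeks 7-8 recalls) − (run-in recalls). The second term precedes randomisation and the first follows it, so the change score is partly post-randomisation. Run-in diet alone is not.

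**2. Which models would admit it.** The feature models would not, because their covariates are baseline variables. The Aim 3 list does not include diet. The Shannon model and the SCFA models have unlisted vectors, so nothing in them keeps dietary change out.

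**3. What adjustment would do.** Let A be arm (0/1), D dietary change, Y the outcome, and U an unmeasured cause of both D and Y with variance 1. Take D = aA + uU + error, scaled so that D has variance 1 within arm, and Y = dA + bD + uU + error.

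- Unadjusted coefficient of A: d + ab, the total effect.
- Within-arm slope of Y on D: b + u².
- Coefficient of A adjusted for D: (d + ab) − a(b + u²) = d − au².
- Difference between the two: ab + au². The first term is the mediated part removed (a change from total to direct effect). The second is collider bias.

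**4. Illustration.** Every path size below is an assumption, because the documents give none. The total effect is fixed at 0.50 in standardised units, so d = 0.50 − ab.

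| a | b | u | Direct effect d | Adjusted estimate d − au² | Mediated part removed, ab | Collider bias, au² |
|---|---|---|---|---|---|---|
| 0 | any | any | 0.50 | 0.50 | 0 | 0 |
| 0.2 | 0 | 0.5 | 0.50 | 0.45 | 0 | 0.05 |
| 0.2 | 0.3 | 0 | 0.44 | 0.44 | 0.06 | 0 |
| 0.2 | 0.3 | 0.5 | 0.44 | 0.39 | 0.06 | 0.05 |
| 0.5 | 0 | 0 | 0.50 | 0.50 | 0 | 0 |
| 0.5 | 0 | 0.5 | 0.50 | 0.375 | 0 | 0.125 |
| 0.5 | 0.3 | 0 | 0.35 | 0.35 | 0.15 | 0 |
| 0.5 | 0.3 | 0.5 | 0.35 | 0.225 | 0.15 | 0.125 |

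A simulation with 100,000 per arm agrees with these adjusted values to about 0.01, and its unadjusted estimate stays at about 0.50 throughout.

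Adjustment is harmless for the total effect when a = 0, or when diet neither affects the outcome nor shares causes with it (b = u = 0). All rows with a discrepancy show attenuation because the assumed paths are positive. With a = 0.5, b = −0.3 and u = 0, d = 0.50 + 0.15 = 0.65 and the adjusted estimate is 0.65, so the direction is not fixed either.

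**The case against.** The strongest reply is that no specified analysis adjusts for dietary change. Sections 3.2 and 5.2 explain why diet is measured and what the recalls make possible; the models are in 15.3, where diet does not appear. The Shannon model's conditional vector, read beside the baseline group comparisons in 15.1, can naturally be taken to mean chance baseline imbalance, and Aim 2 is introduced as following Aim 1. This stands in part. A reader might infer that the plan commits the primary models to adjustment for dietary change, and the documents do not support that. Equally, they do not exclude it: only the feature models are limited to baseline, and the two earlier sections state the adjustment as the purpose of collecting the data.

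Second, the design tries to keep diet constant. Eligibility requires willingness to maintain current diet, and a personal three-day meal plan with a checklist precedes each stool sample. If this works and exercise does not shift diet, dietary change is merely prognostic: adjusting for it causes no bias and may gain precision. That stands. A reader might infer that dietary change must be either a mediator or a collider here; it need not be. But the meal plan covers days 3 to 5 and the assessment visit, with its fasting draw, is on day 7 (Table 1), so these safeguards reduce the risk to the SCFA outcome without removing it.

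Third, dietary change may legitimately matter in Aim 3. Randomisation does not protect the relation between microbiome or SCFA change and CMDrisk, and diet could confound it. That stands, and it is a reason not to drop dietary change from the analysis altogether.

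**Conclusion.** The concern holds as a conflict between a stated intention and the randomised comparison it would be applied to. The reason given for controlling dietary change is wrong for Aims 1 and 2, and 15.3 leaves both sets of primary models open to it. Whether the adjustment would reach those models is undetermined.

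Harm requires two conditions: exercise alters diet, and diet affects the outcome or shares causes with it. The size cannot be computed from the documents. A reader might infer a definite percentage loss from the illustration. It supports none: it runs from no change to 0.225 against a total of 0.50, depending on assumed paths. In the cases with b = 0.3, more than half of the shift is the move from total to direct effect, and only the remainder is collider bias. The conclusion assumes that the target in Aims 1 and 2 is the total effect of assignment, as the aims are worded.

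**What to change.** In 15.3, state that the primary Aim 1 and Aim 2 models adjust only for named variables measured before randomisation, for example the baseline value of the outcome and run-in diet. This matches the baseline restriction already placed on the feature models.

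In 3.2 and 5.2, say that dietary change will be reported by arm and used only in labelled sensitivity or exploratory models. If it is wanted in Aim 3 as a mediator-outcome confounder, add it there explicitly and state the assumptions, including whether exercise is taken to leave diet unaffected.

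The cost is wording in three sections and no new data. If dietary change is prognostic and unaffected by arm, leaving it out of the primary models may lose a little precision.

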4.0 Study Intervention(s)/Investigational Agent(s)

4.1 **Description:** Following baseline data collection, participants will be randomized into one of two study groups using PROC PLAN (SAS 9.4) and a 1:1 allocation ratio.

GROUP 1 (aka, Experimental group): participants will complete 3 walking sessions/week for a total of 8 weeks (24 total sessions). Walking sessions will either take place on new commercial treadmills in the Epidemiology Clinical Research Center or remotely at or around a participant's home (see below). Regardless of the walking location, walking sessions will be 30 min in duration during intervention weeks 1 through 4 and a minimum of 45 min each during intervention weeks 5 through 8.

GROUP 2 (aka, Control group): participants will be asked to maintain their usual PA during the initial 8-week intervention period but will undergo all data collection procedures as outlined for the experimental group (See Section 5.2).

Experimental group participants who want to forego in-person exercise sessions on the University of Minnesota campus due to logistical constraints or the COVID-19 pandemic will modify the exercise intervention in the following manner:

MEDICAL PROTOCOL (HRP-590)

PROTOCOL TITLE: Exercise and the Gut Microbiome R21

VERSION DATE: 05/11/2022

Experimental group participants will engage in the same frequency and duration of walks as described above, but with a change in location to either: (a) in neighborhood or backyard walk (weather permitting, maintaining physical distancing); (b) on a treadmill within their home; and (c) in the hallway of their home if options a. and b. are not possible.

To monitor physical activity levels and ensure remote compliance: we will monitor to ensure that participants are completing their home-based walks at the proper duration and intensity using the Fitabase® platform. (See more information on the data security of Fitabase® in Section 16.7)

4.2 **Drug/Device Handling:** N/A

4.3 **Biosafety:** N/A

4.4 **Stem Cells:** N/A

5.0 **Procedures Involved**

5.1 **Study Design:** We will employ a 100-participant, 8-wk, randomized 2-arm parallel trial design with a 1:1 allocation ratio.

5.2 **Study Procedures:** All eligible and consented participants will complete a 3-week run-in phase during which baseline outcome assessments will be performed. During run-in weeks 1 and 2, participants will wear a Fitbit Inspire 2 smartwatch and complete three unannounced dietary recalls. During the run-in week 3 (see table below), participants will consume their 3-day standardized meal plan on days three through five, obtain a fecal sample, and complete a study assessment visit. To quantify compliance with the 3-day meal plan, participants will be provided with a paper checklist of all foods to be consumed, and will be asked to indicate which foods were consumed and to document any deviation. The study assessment visit will include a fasting blood draw, blood pressure in triplicate, weight measure and body fat assessment in duplicate, and a saliva sample. Following successful completion of all measures, participants will then be randomized into one of the two study groups using PROC PLAN (SAS 9.4) and a 1:1 allocation ratio.

Group 1 (Experimental group): Participants will complete 3 treadmill walking sessions/week (24 total sessions) over 8 weeks at or around their home or in-person within the Epidemiology Clinical Research Center. Each walking sessions will be 30 min in duration during intervention weeks 1

MEDICAL PROTOCOL (HRP-590)

PROTOCOL TITLE: Exercise and the Gut Microbiome R21

VERSION DATE: 05/11/2022

through 4 and 45 min during intervention weeks 5 through 8. Notably, this exercise dose (i.e., intensity x session duration x weekly frequency x intervention length) is equivalent to, or greater than, that employed in most existing human studies of exercise and the gut microbiome in addition to the exercise dosage observed necessary to yield meaningful cardiometabolic changes.⁷² Therefore, while the dose is 'modest', it reflects what is relevant in real-world interventions and appropriate for overweight or obese sedentary individuals.

During week 4, participants will again consume their 3-day standardized meal plan, obtain a fecal sample, and complete a study assessment visit (same measures as described above for the 3-week run-in, except no fasting blood draw will be taken).

During weeks 7 and 8, participants will complete 3 unannounced phone-based dietary recalls. During week 8, participants will again consume their 3-day standardized meal plan, obtain a fecal sample, and complete a study assessment visit (same measures as described above in run-in week 3).

Table 1. Timing of Data Collection events during the 3-Week Run-In and Intervention Weeks 4 & 7/8.

Day 1	Day 2	Day 3	Day 4	Day 5	Day 6	Day 7
				Stool (pm)*	Stool (am)*	Stool
		Standard Diet Day1	Standard Diet Day2	Standard Diet Day3		
						Assess. Visit

**Preferred timing stool collection is the evening of Day 5 or morning of Day 6, though anytime in the Day 5 – 7 window is acceptable.*

Group 2 (Control group): Participants will be asked to maintain their usual PA during the initial 8-week intervention period but will undergo all data collection procedures as outlined above for the experimental group.

Expanded Data Collection Procedures: We have two **Primary Outcomes**.

The first primary outcome is changes to the gut microbiome, assessed via metagenomic sequencing, from pre- to post-intervention (**Specific Aim 1**). The Shannon Index will be our primary indicator for changes in gut microbiota composition. Participants will use the OMNIgene-Gut stool collection kit to obtain their fecal samples collected at baseline, week 4 and

MEDICAL PROTOCOL (HRP-590)

PROTOCOL TITLE: Exercise and the Gut Microbiome R21

VERSION DATE: 05/11/2022

week 8. The home-collected samples will be returned to our lab within 30 days. DNA will be extracted from the stool samples using the 96 well plate Mo Bio Power soil kit on an Epmotion robot and eluted into 50ul aliquots. Each extraction will contain negative and positive controls representing defined bacterial communities (Zymo; Irvine, CA). DNA will be quantified using Quant-it and stored at -80°C. Metagenomic libraries will be prepared at the *UMN Genome Center* (see 'Facilities' document) using the Nextera XT kit (Illumina; San Diego, CA) and barcoded. DNA libraries will be denatured with NaOH and diluted to 8-12 pM in Illumina's HT1 buffer, spiked with 1% PhiX and a HiSeq 1x100 cycle v3 kit Illumina HiSeq, with an expected output of at least 0.5 million total sequences per sample. This approach has been shown to be valid⁵⁴ and represents an approach that can address both gut microbial taxonomy and community functional content at a cost similar to 16S studies.

The second primary outcome is serum SCFA levels. Participants will undergo fasted blood draws to assess serum SCFA levels (**Specific Aim 2**). This work will be performed using the Metabolon pipeline.⁵⁷ Briefly, serum samples are spiked with a solution of eight stable labelled internal standards and subjected to protein precipitation. After centrifugation, an aliquot of the supernatant is derivatized. The reaction mixture is analyzed by LC MS/MS on an Agilent 1290/ AB Sciex 5500 system. Peak areas of the respective analyte product ions are measured against the peak area of the corresponding internal standard product ions. Quantitation is performed using a weighted least squares regression analysis generated from fortified calibration standards prepared immediately prior to each run.

We have several **Secondary Outcomes**. For **Specific Aim 3** cardiometabolic profiles will be assessed via assays for high-density lipoprotein cholesterol (HDL-C), triglycerides, fasting insulin/glucose, and c-reactive protein (CRP). All blood assays will be conducted by the *UMN Advanced Research and Diagnostic Laboratory* (see 'Facilities' document). Blood samples collected will be stored at -80°C prior to batch-processing. Resting blood pressure (BP) will be taken using an Omron Automatic BP Cuff (Omron; Lake Forest, IL), with the average of the last two BP measurements reported. These cardiometabolic indices form the foundation of the 'metabolic syndrome',⁵⁹⁻⁶³ and we will form a composite continuous score for cardiometabolic disease risk from HDL-C, fasting glucose, triglycerides, the average of systolic and diastolic BP. Specifically, z-scores for each biomarker will be calculated and the within-participant average across z-scores computed and referred to as *cardiometabolic disease risk (CMDrisk*; the primary dependent variable for Specific Aim 3). This score has been used in epidemiologic, experimental, and clinical studies.^{62,64-67} Individual components will be described in secondary analyses as needed. We will also measure HbA1c using standardized procedures and the blood

MEDICAL PROTOCOL (HRP-590)

PROTOCOL TITLE: Exercise and the Gut Microbiome R21

VERSION DATE: 05/11/2022

collected. The oral microbiome will be assessed using a widely employed salivary testing technique. Participants will be asked to drool into a 50mL tube until 5mL of saliva is collected. For participants that are having difficulty generating saliva, we will ask those participants chew a small piece of orthodontic wax for 5 minutes and then drool into the 50mL tube. We have experience with this non-invasive assessment⁶⁹, with the assessment taking no longer than 5-10 minutes overall and presenting no greater than minimal risk. Other secondary outcomes are necessary to measure to ensure we can properly control for confounding. Dietary composition will be assessed via 3 phone-based dietary recalls. These recalls will be performed on 2 weekdays and 1 weekend day by trained interviewers. Assessment of diet on multiple days allows us to capture the individual variation in participants' diets.⁷¹ We will use these dietary recalls to develop personalized 3-day meal plan to standardize individual dietary behavior prior to stool sample collection. Although randomization should lead to approximately balanced groups with respect to diet, employing dietary recalls at these time points will allow us to adequately statistically control for participants' dietary changes—changes which, if not controlled, might confound study results.^{70,71} Physical activity will be measured during the duration of the study using the Fitbit Inspire 2 smartwatch. Finally, anthropometric outcomes will include height measured using a Seca stadiometer (Seca; Hamburg, Germany), with weight and body composition measured using the Tanita TBF-300a Body Composition Analyzer (Tokyo, Japan).

To collect blood samples and saliva samples as well as body weight, body fat percentage, and blood pressure, we are proposing to employ the following procedures in the designated settings while following all necessary COVID-19 precautions:

Setting: Baseline, week 4, and week 8 visits will occur in the Epidemiology Clinical Research Center (ECRC). We will follow all UMN, OVPR and ECRC approved guidelines for conducting research during the COVID-19 pandemic.

COVID-19 Screening: Participants will complete the OVPR-approved ECRC COVID-19 phone screener the day prior to their visit. Prior to entering the ECRC, participants will call the study coordinator and complete the screening questionnaire again. Upon entry into the building, study staff will assess the participant's temperature.

- **Personal Protective Equipment (PPE):** Participants will be asked to wear a mask. All ECRC staff coming within 6 feet of study participants (e.g. for blood or blood pressure collection) will be adhering to UMN guidelines for PPE (e.g. masks, gloves).

MEDICAL PROTOCOL (HRP-590)

PROTOCOL TITLE: Exercise and the Gut Microbiome R21

VERSION DATE: 05/11/2022

ECRC Data Collection:

- Each participant will be directed to a well-ventilated exam room, outfitted with a HEPA air purifier for additional protection where all non-lab measurements will take place.
- Participant will step upon the study scale and state to us their weight and body fat percentage while we stand at least 6 feet away. No other participants will be in the exam room, so confidentiality will be assured.
- Study staff will obtain blood pressure and a trained phlebotomist will collect the blood samples. As always, juice and snacks will be on hand in case needed after the blood draws. We will then have participants collect their saliva samples.
- Participant will be directed out of the building. Blood samples will be processed immediately and placed into a -80 freezer.
- We will thoroughly disinfect all touchpoints and research materials while properly disposing of biohazards.

If ECRC visits cannot occur due to continued COVID-19 outbreaks, we will conduct Home-Based Visits in the following manner:

- Participants will complete the OVPR-approved ECRC COVID-19 phone screener the day prior to their visit.
- Upon staff arrival, study staff will call the participant to again complete the OVPR-approved ECRC COVID-19 phone screener, and a temperature reading of the participant will be taken when they come outside.
- The scale platform will be placed outside the participant's home on a flat surface. The scale reader is connected to the platform by a 6 foot cord, enabling the staff to read the output while maintaining physical distance.
- Blood pressure will be obtained by the study staff member completing the research session.
- The study phlebotomist will collect the blood samples with participant seated in the chair. Juice and snacks will be made available in case the need arises. Blood will be placed in a cooler with dry ice for transport back to the ECRC for processing and placement into a -80 freezer.
 - We will also thoroughly disinfect all touchpoints and research materials while properly disposing of biohazards.

We have outlined the procedures we will take to ensure participant safety during the intervention within section 13.1. This study presents no greater than minimal risk to participants. All data collection forms are available on ETHOS.

MEDICAL PROTOCOL (HRP-590)

PROTOCOL TITLE: Exercise and the Gut Microbiome R21

VERSION DATE: 05/11/2022

5.3 **Study Duration:** The total duration of study participation will be approximately 11 weeks from initial contact with the researchers to the conclusion of all study procedures.

As for the data analyses associated with this study, we anticipate these data analyses to take approximately 4 months—allowing time for the *UMN Genomics Center* and the *UMN Advanced Research and Diagnostic Laboratory* to batch process participants' stool samples and blood work, respectively.

5.4 **Individually Identifiable Health Information:** Each participant will be assigned a unique study ID that will consist of a series of numbers and letters that will have no meaning to any of the individual's personal identifying characteristics. The investigators will use this ID to track each individual participant in the research database. There will be no identifiers in this database. The identifiers will be maintained in separate, secure, encrypted, password-protected database in a different physical location. This separate database for the identifying information will also include the study ID so that the investigators can link research data to individuals when necessary.

5.5 **Use of radiation:** N/A

5.6 **Use of Center for Magnetic Resonance Research:** N/A

